10 TREATMENTS

10.1 Overview of Treatments Administered

Subjects will take FLX475 orally once daily (QD) starting on Day 1 of Cycle 1. See [Section 10.2.1](#) for details of the planned dose administration schema.

Subjects will also receive ipilimumab. Ipilimumab 3 mg/kg will be administered IV Q3W for up to four doses.

The treatments to be used in this study are outlined in [Table 1](#).

Table 1 Study Treatments

Study Treatment	Formulation	Dose Levels	Route of Administration	Sourcing
FLX475	Tablets	100 mg (with possible dose reduction to 75, 50, or 25 mg) qd	Oral	Provided centrally by the Sponsor
Ipilimumab	Solution for infusion	3 mg/kg Q3W	IV infusion	Provided by the site

IV = intravenous, Q3W = once every 3 weeks, qd = once daily.

10.2 FLX475 Administration

All subjects will take FLX475 orally once daily on a continual basis. On days when ipilimumab is also administered (i.e., Day 1 of Cycles 1–4), FLX475 should be taken approximately 1 hour before the ipilimumab infusion.

The dose administration schema for FLX475 is provided below, along with instructions for dose modification.

10.2.1 Dosing Plan

As noted in [Section 6.1.4](#), the recommended Phase 2 dose of FLX475 of 100 mg PO QD has been selected both for monotherapy and for combination therapy with pembrolizumab in study FLX475-02. Therefore, this same dose will be used in this study in combination with ipilimumab. Should the safety run-in safety data suggest that the 100 mg of FLX475 dose is not acceptable in combination with ipilimumab, a lower dose (e.g. 75 or 50 mg PO QD) may be chosen to be used after evaluation in a new safety run-in cohort of six subjects. In the event of a change in FLX475 dose, additional subjects may be enrolled to ensure that a minimum of 20 subjects are treated at the chosen combination dose regimen.

After all subjects in the safety run-in phase have completed the 3-week safety observation period, a Safety Review Committee (SRC) will be convened. The SRC members will be composed of appropriate Sponsor and CRO representatives, including the Sponsor's medical

monitor or designee(s), safety officer or designee, and clinical trial managers (CTMs). Additional members may be added as needed (e.g., PK scientist, and/or biostatistician). The SRC will carefully consider all available safety, laboratory, and PK information in consultation with the study investigators. After review of all available data, and if the safety profile of the combination therapy is deemed acceptable, the SRC will recommend continuation of the study and enrollment of the remainder of the subjects. If the safety profile of the combination regimen is not deemed to be acceptable (e.g. DLT observed in > 1 of 6 subjects), the SRC may recommend de-escalation of FLX475 to a lower dose (e.g. 75 or 50 mg PO QD); de-escalation of ipilimumab to a lower approved dose (e.g. 1 mg/kg); delay, or termination of dosing. Beyond the safety run-in, the SRC will continue to meet at least quarterly during the study to review accumulating safety data and may also recommend an amendment to the protocol to evaluate alternate study drug administration schedules or other changes in study design as may be appropriate based on emerging clinical data.

10.3 Ipilimumab Administration

Ipilimumab 3 mg/kg will be administered as an IV infusion over 30 or 90 minutes (per institutional protocol) on Day 1 of the first four 3-week treatment cycles (i.e., 21 days [\pm 3 days]) after all procedures and assessments have been completed, including any 1 hour post-FLX475 dose procedures, approximately 1 hour after the Day 1 dose of FLX475.

The investigational staff should make every effort to ensure that the infusion duration be as close to 30 or 90 minutes as possible. However, given the variability of infusion pumps from site to site, a window between -5 minutes and + 10 minutes is permitted.

Ipilimumab should be prepared and administered per standard institutional protocol and the approved label instructions.

10.4 Dose-Limiting Toxicity and Stopping Criteria

The safety profile of ipilimumab monotherapy has been well described ([Yervoy® Package Insert](#)) and includes a significant number of immune-related adverse events (irAEs) to be taken into account when determining what might be either unexpected or unacceptable toxicity for the combination of FLX475 with ipilimumab. Therefore, a DLT for this study will be defined as an AE or abnormal laboratory value assessed by the investigator as possibly, probably, or definitely related to study treatment, excluding toxicities clearly not related to study treatment, such as PD, environmental factors, unrelated trauma, etc. occurring during Days 1–21 of Cycle 1 (“DLT Observation Period”), that meets any of the following criteria:

- Grade 4 hematological laboratory abnormality lasting \geq 7 days, except thrombocytopenia, or:
 - Grade 4 thrombocytopenia of any duration; or
 - Grade 3 thrombocytopenia associated with clinically significant bleeding

- Nonhematological Grade 3 or 4 laboratory abnormalities:
 - Clinically significant medical intervention is required to treat the subject, or
 - The abnormality leads to hospitalization, or
 - The abnormality persists for >1 week, or
 - The abnormality results in a Drug-induced Liver Injury (DILI)
 - Exceptions: Clinically nonsignificant, treatable, or reversible laboratory abnormalities including liver function tests, uric acid, etc.
- Any Grade 4 non-hematologic AE of any duration, with the following exception:
 - Grade 4 diarrhea lasting 48–72 hours in subjects who have received suboptimal anti-diarrheal therapy
 - Grade 3 rash that does not resolve to Grade 1 or baseline level (whichever is higher) within 14 days with adequate medical management
 - Grade 3 fever that does not resolve to Grade 1 or baseline level (whichever is higher) within 14 days with adequate medical management
 - Grade 3 fatigue that does not resolve to Grade 2 or baseline level (whichever is higher) within 14 days with adequate medical management
 - Grade ≥ 3 creatinine increase
 - Grade 3 nausea, vomiting, colitis, or diarrhea requiring total parenteral nutrition or hospitalization (e.g., duration >48 hours despite optimal management) that does not resolve to Grade 1 or baseline level (whichever is higher) within 14 days
 - Grade 2–3 uveitis, eye pain, or blurred vision that does not respond to topical therapy and does not improve to Grade 0 or 1 within 14 days
 - Grade ≥ 2 nonhematological toxicity requiring systemic immunosuppressive therapy. This includes, but is not limited to, autoimmune diseases of the lung, heart, kidney, bowel, CNS, pituitary, or eye
 - Grade ≥ 2 endocrine toxicity requiring hormone replacement, with the exception of Grade 2 thyroiditis and thyroid dysfunction (which are acceptable)
 - Grade ≥ 3 adrenal insufficiency
 - Grade ≥ 3 febrile neutropenia:
 - Grade 3 is defined as absolute neutrophil count (ANC) $< 1000/\text{mm}^3$ with a single temperature of $> 38.3^\circ\text{C}$ (101°F) or a sustained temperature of $\geq 38^\circ\text{C}$ (100.4°F) for more than 1 hour

- Grade 4 is defined as ANC < 1000/mm³ with a single temperature of > 38.3°C (101°F) or a sustained temperature of ≥ 38°C (100.4°F) for more than 1 hour, with life-threatening consequences and urgent intervention indicated
- QTcF interval ≥ 501 msec and > 60 msec prolongation from baseline (defined as the average QTcF value from pre-dose C1D1 ECGs), or associated with Torsades de pointes, polymorphic ventricular tachycardia, or serious arrhythmia
- Prolonged delay (> 2 weeks) in initiating Cycle 2 due to treatment-related toxicity;
- Any treatment-related toxicity that causes the subject to discontinue treatment during Cycle 1.
- Any Grade 5 toxicity.

Refer to the National Cancer Institute (NCI) Common Terminology Criteria for Adverse Events (CTCAE), Version 5.0 ([Appendix 1](#)) for grading of the severity of AEs and laboratory abnormalities.

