As part of a safety run-in, the first six subjects on study will be treated with both the recommended Phase 2 dose of FLX475 (100 mg PO QD) and the approved dose of ipilimumab (3 mg/kg IV) and observed for a minimum of one cycle of treatment (21 days) for any unacceptable toxicities (dose-limiting toxicities or DLTs as described in [Section 10.4](#)) prior to enrolling additional subjects. A DLT can be observed in no more than one of the first six subjects during the first cycle of treatment before enrollment of the remainder of the study subjects can continue. If a treatment-related DLT is observed during the first cycle of treatment in more than one of the first six (or fewer) subjects, dose modification of either or both drugs will be considered by the Safety Review Committee prior to continuing enrollment, potentially in an additional safety run-in.

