Any subjects in the safety run-in phase who do not receive at least 80% of planned doses in Cycle 1 due to reasons other than DLT, or who stop treatment prior to completing evaluation for the initial 3 weeks of therapy (DLT Observation Period) due to PD or refusal to participate further for reasons other than DLT, will be replaced at that dose level to permit full evaluation of the safety run-in. See [Section 10.4](#) for the definition of a DLT.

9.1.4 *Removal of Subjects from Therapy or Assessment*

Discontinuation of study treatment does not represent withdrawal from the study.

The investigator may discontinue treating a subject with study treatment or withdraw the subject from the study at any time for safety or administrative reasons, but should inform or discuss with the Sponsor's medical monitor prior to doing so (when feasible). The subject may decide to discontinue study treatment or withdraw from the study at any time for any reason.

The reason for discontinuation of FLX475, ipilimumab, or both will be documented. If a subject discontinues study treatment, the subject will enter the Follow-Up Phase and complete protocol-specified End-of-Treatment and Follow-up visits, procedures, and survival follow-up, unless the subject withdraws consent. The investigator should confirm whether a subject will discontinue study treatment but agree to continue protocol-specified, post-treatment study visits, procedures, and survival follow-up, or whether the subject withdraws consent or is lost to follow-up. If a subject withdraws consent, the date will be documented in the source documents. The investigator, or designee, will complete the appropriate eCRF, indicating the primary reason for discontinuation. In addition, the date of final dose of study treatment(s) will be recorded on the appropriate eCRF.

All subjects who discontinue study treatment without having PD will continue to undergo tumor assessments using the same imaging schedule used during the Treatment Phase (i.e., every 9 weeks [± 1 week] in Year 1 or every 12 weeks [± 1 week] beyond Year 1) until the start of a new anticancer treatment, disease progression, pregnancy, or the end of the study, whichever occurs first, unless the subject withdraws consent, is lost to follow-up, or dies.

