10.5.1 FLX475

For ongoing DLT assessment throughout both parts of the study, subjects will be monitored closely for treatment-emergent AEs (TEAEs) and laboratory abnormalities. [REDACTED]

[REDACTED]

[REDACTED]

If a subject experiences an AE, appropriate supportive care (e.g., antiemetics, antidiarrheals) should be instituted according to the nature of the event. In general, dose modifications of FLX475 are not permitted during the DLT Observation Period (Days 1–21 of Cycle 1). Subjects who experience a DLT during Cycle 1 should discontinue study treatment (unless it is determined to be in the subject's best interest to continue treatment by the investigator in consultation with the Sponsor's medical monitor).

For subjects receiving study treatment beyond Cycle 1, the following dose modification and discontinuation guidelines for FLX475 below should be considered. (Note that AEs known to be associated with ipilimumab but not previously observed with FLX475 monotherapy may not require modification of FLX475 dose.)

- For any clinically-significant organ-related Grade 4 TEAE (neurologic, pulmonary, cardiac, gastrointestinal, genitourinary, renal, hepatic, cutaneous) at least possibly related to FLX475, discontinue drug use permanently (unless it is determined by the investigator, in consultation with the Sponsor's medical monitor, to be in the subject's best interest to continue treatment, at a reduced dose).

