- ^c Vital signs (blood pressure, pulse, respiratory rate, and temperature) will be collected with the subject in a sitting position. Vital signs will be assessed at Screening Visit, pre-dose and at 0.5, 1, 2, and 4 hours post-dose on Cycle 1, Day 1; pre-dose and 2 hours post-dose on Cycle 1, Days 8 and 15; pre-dose and at 0.5, 1, 2, and 4 hours post-dose on Cycle 2, Day 1. Vital signs will also be assessed pre-dose on Day 1 of all subsequent cycles and at Early Discontinuation / End of Study Treatment (ED/EOST). Acceptable windows for collection are as follows: pre-dose samples must be within 6 hours prior to dosing; 0.5 hour post-dose \pm 5 minutes; 1 hour post-dose \pm 15 minutes; 2 and, 4 hour post-dose \pm 30 minutes.
- ^f Triplicate ECGs with tracings \geq 30 seconds apart must be collected in digital format on designated calibrated ECG equipment after at least 10 minutes of quiet rest in supine position. Meals should not be served shortly before ECGs. Triplicate ECGs should be collected at Screening Visit; -0.75, -0.5, and -0.25 hours pre-dose and 2 and 4 hours post-dose on Cycle 1, Day 1; pre-dose and 2 hours post-dose on Cycle 1, Day 8; pre-dose and 2 hours post-dose on Day 1 of Cycles 2-6; and at Early Discontinuation / End of Study Treatment (ED/EOST). Acceptable windows for collection are as follows: general pre-dose ECGs must be within 2 hours prior to dosing; -0.75, -0.5, -0.25 hour pre-dose \pm 5 minutes; 2 and 4 hour post-dose \pm 30 minutes.
- ^g Serum Chemistry: including sodium, potassium, chloride, total protein, bicarbonate, albumin, calcium, magnesium, phosphorous, glucose, BUN, creatinine, total bilirubin, ALP, LDH, AST, ALT, amylase and lipase. Serum Chemistry to be collected at Screening Visit, pre-dose (within 24 hours prior to dosing) on study visit days, and at Early Discontinuation / End of Study Treatment (ED/EOST).
- ^h Complete Blood Count and Differential: WBC, RBC, ANC, hemoglobin, hematocrit, MCV, MCH, platelets, and WBC differential. CBC with differential to be performed at Screening Visit, pre-dose (within 24 hours prior to dosing) on study visit days, and at Early Discontinuation / End of Study Treatment (ED/EOST).
- ⁱ Coagulation Tests should be obtained at Screening Visit and pre-dose (within 24 hours prior to dosing) for Day 1 visits of Cycles 1-2 and at Early Discontinuation / End of Study Treatment (ED/EOST): PT, PTT or aPTT, and INR.

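### The laboratory DLT exception for treatable or reversible abnormalities has no limit, so it exempts some Grade 3 events that the same bullet counts

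*Protocol*

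**What the plan says.** Protocol 10.4 defines a DLT as a treatment-related event on Days 1–21 of Cycle 1 that meets any item on a list; the synopsis carries essentially the same list. One item covers Grade 3 or 4 nonhematological laboratory abnormalities. It counts them on any of four criteria: clinically significant intervention, "The abnormality leads to hospitalization", "The abnormality persists for >1 week", or DILI. The last line under the same item reads "Exceptions: Clinically nonsignificant, treatable, or reversible laboratory abnormalities including liver function tests, uric acid, etc". Synopsis and body use the same words for this item.

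Other items on the list are independent of that exception. They include Grade 4 non-hematologic AEs, Grade 3 or higher creatinine increase, Grade 2 or higher "nonhematological toxicity requiring systemic immunosuppressive therapy", related toxicity that ends treatment in Cycle 1, and a delay of more than 2 weeks in starting Cycle 2.

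The label is used in two main places:

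- **Run-in limit.** Protocol 6.2: "A DLT can be observed in no more than one of the first six subjects during the first cycle of treatment". Beyond that, the Safety Review Committee (SRC) considers dose modification.
- **Individual treatment.** Protocol 10.5.1: "Subjects who experience a DLT during Cycle 1 should discontinue study treatment", unless the investigator, in consultation with the medical monitor, finds that continuing is in the subject's best interest.

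SAP 7.5.2 tabulates the incidence of any DLT. The SAP gives no DLT definition of its own.

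**The concern.** The three terms in the exception are joined by *or*, so an abnormality that is merely treatable, or merely reversible, is exempt. Neither term is defined or limited in time. Most laboratory abnormalities that bring a patient into hospital can be treated, and most that last more than a week eventually reverse. The exception therefore reaches the events that the criteria above it were written to count.

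The run-in is the only formal safety gate before the rest of the approximately 20 subjects are enrolled, and it turns on a count where one subject matters: one DLT in six is within the limit and two is not. Two investigators applying the same sentence to the same event could report different counts.

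**Working it through.** **Step 1. Apply both parts of the bullet to specific events.** Each event is assumed to be related, Grade 3 and in Cycle 1. Electrolytes and "AST, ALT, amylase and lipase" are in the serum chemistry panel drawn on study visit days (Table 6 footnote), so such events would be seen.

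| Event | Counted by | Exempted by |
|---|---|---|
| Electrolyte abnormality that leads to hospitalization and is corrected | Hospitalization; probably also intervention | Treatable; reversible |
| Lipase rise that lasts 10 days and then normalizes | More than 1 week | Reversible |

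The first is the cleaner case. The second could also be spared as clinically nonsignificant if it is asymptomatic.

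**Step 2. Try each order of precedence.**

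- If the exception prevails, the intervention, hospitalization and one-week criteria catch little beyond untreatable or irreversible abnormalities.
- If the criteria prevail, the words treatable and reversible do almost nothing.

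Neither order leaves both parts with a sensible job. Neighbouring items are bounded: the Grade 4 diarrhea exception is tied to 48–72 hours, and rash, fever and fatigue to 14 days.

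**Step 3. Size, given one such event.** The documents state no operating characteristic for the run-in, so there is no figure to reproduce. Let *p* be a subject's risk of an undisputed DLT, independent across subjects and of the disputed event (assumed). One of six subjects has a disputed event. The reading changes the outcome only if that subject has no undisputed DLT, probability (1 − p), and exactly one of the other five does, probability 5p(1 − p)^4. The product is 5p(1 − p)^5:

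| p (assumed) | Calculation | Reading decides |
|---|---|---|
| 5% | 0.25 × 0.95^5 | 19.3% |
| 10% | 0.50 × 0.90^5 | 29.5% |
| 20% | 1.00 × 0.80^5 | 32.8% |
| 30% | 1.50 × 0.70^5 | 25.2% |

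**Step 4. Size, before knowing whether such an event occurs.** Let *q* be the chance of a disputed event in a subject without an undisputed DLT. The probability that the reading decides is P(at least 2 of 6 at risk p + (1 − p)q) − P(at least 2 of 6 at risk p). For p = 10% and q = 5%, the first risk is 0.10 + 0.90 × 0.05 = 0.145, giving 21.18% − 11.43% = 9.76% from unrounded values. All entries rest on assumed p and q:

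| q | p = 5% | p = 10% | p = 20% | p = 30% |
|---|---|---|---|---|
| 1% | 1.25% | 1.81% | 1.97% | 1.50% |
| 2% | 2.65% | 3.71% | 3.93% | 2.97% |
| 5% | 7.66% | 9.76% | 9.75% | 7.23% |
| 10% | 17.91% | 20.58% | 19.10% | 13.73% |

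**The case against.** The best reply is that an exception ordinarily overrides the rule it sits under, so the bullet has one answer: these events are not DLTs. That is a fair reading, but it does not rescue the rule. A Grade 3 electrolyte abnormality serious enough for hospital admission would then not count, although hospitalization is a stated criterion. The defect moves from ambiguity to an exception that empties the criteria it qualifies.

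Several limits on the point do stand.

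- **Liver tests.** Because the exception names liver function tests and the criteria name DILI, a reader might infer that Grade 3 transaminase rises commonly fall into the gap. The documents do not support this. Table 4 directs corticosteroids and permanent ipilimumab discontinuation for Grade 3 or 4 AST/ALT elevation, so most such events would be caught by the immunosuppression or discontinuation items.
- **Replacement.** Protocol 9.1.3 replaces run-in subjects "who do not receive at least 80% of planned doses in Cycle 1 due to reasons other than DLT", and a reader might infer that the same subject could be a DLT or a replacement depending on the reading. That needs at least 5 of 21 FLX475 doses missed (80% of 21 is 16.8), while 10.5.1 generally does not permit FLX475 dose modification in Cycle 1. It is too strained to rely on.
- **Frequency.** Nothing in the documents supports the upper values of q. In protocol 6.1.3.2, the monotherapy DLTs were QTc events, no DLTs occurred with pembrolizumab, and healthy volunteers had no significant laboratory abnormalities. None of this covers ipilimumab.
- **Consequence.** Crossing the limit means that modification is considered. Protocol 10.2.1 gives more than one in six only as an example, and the SRC reviews all safety and laboratory data whatever the label.
- **Intent.** The sponsor evidently wants to spare laboratory changes of no clinical relevance. Table 2, footnote e, sends such amylase and lipase rises to discussion. A fix should respect that.

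**Conclusion.** The exception is wrong as written, and the point is minor. It affects some Grade 3 nonhematological laboratory events, mainly electrolytes, amylase and lipase. It does not undermine the DLT definition as a whole, although a reader might infer that from the breadth of the wording: the other items on the list still operate.

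Given one such event, the reading decides whether the one-in-six limit is exceeded in about 19% to 33% of cases. This assumes independent subjects and an undisputed DLT risk of 5% to 30%. It is a conditional figure. The overall chance depends on an event rate that the documents do not give, and is about 1% to 4% if that rate is 1% to 2%. SRC review and the medical-monitor consultation soften the practical effect but do not settle how the event is classified.

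A reader might also infer that the SAP's DLT listing should flag exempted events. It could not do so as planned. SAP 7.5.3 lists AEs associated with DLT, and an exempted event is not one. SAP 7.5.4 already lists all laboratory values by subject, with toxicity grades for relevant parameters.

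**What to change.** In protocol 10.4 and the synopsis, replace the exception line with:

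> Exception: clinically nonsignificant Grade 3 laboratory abnormalities that do not require clinically significant medical intervention, do not lead to hospitalization, do not result in DILI, and resolve to Grade 1 or baseline within 1 week. Asymptomatic elevations of named tests (e.g., amylase, lipase, uric acid) may persist beyond 1 week up to a stated limit.

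The sponsor chooses the tests and the limit. The first sentence makes the four criteria prevail. The second keeps room for the laboratory changes the sponsor wants to spare.

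The cost is one line in two places, with no new data and no SAP change. The downside is that a few more Grade 3 laboratory events would count as DLTs, such as an electrolyte abnormality corrected in hospital. SAP 7.7 records that the study stopped early, so the edit may change no run-in decision already made.

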12 STATISTICAL METHODS

12.1 General Statistical Considerations

Tabulations of summary statistics, graphical presentations, and statistical analyses will be performed using SAS® software. Descriptive statistics will be used to summarize data from this study, including mean, standard deviation, median, minimum, and maximum for continuous variables and frequency distributions and percentages for categorical variables. The specifics for these outputs will be described in detail within the Statistical Analysis Plan (SAP), which will be finalized before database lock.

The last observation prior to the first dose of study medication will be used as the baseline value for calculating post-administration changes from baseline. All data obtained on the eCRF will be presented in by-subject data listings.

Confidence intervals will be at the 95% confidence level unless stated otherwise.

Statistical analyses will be performed using SAS® software or other validated statistical software as required. Details of the statistical analyses will be included in a separate statistical analysis plan (SAP), which will be finalized before the database lock.

12.1.1 *Rationale for Sample Size*

The sample size of 20 subjects is considered adequate on clinical grounds to judge the safety of the combination therapy and obtain an initial estimate of its clinical efficacy.

The primary efficacy endpoint will be the overall response rate (ORR). The ORR for the combination therapy is hypothesized to exceed the value observed with ipilimumab monotherapy (10–15%, [Long et al., 2017](#)). A decision to officially expand enrollment beyond the planned approximately 20 subjects will depend on the number of responders in the first 20 evaluable subjects and will require a protocol amendment. To be considered evaluable, subjects must meet criteria for the Efficacy Evaluable population, be evaluable for tumor response as per RECIST v1.1 at 9 weeks, and have no major protocol deviations.

Evaluability for tumor response will be based on the following:

- Subjects who remain on study until the first evaluation (at 9 weeks) and have a tumor assessment performed.
- Subjects who withdraw from the study due to disease progression before the first evaluation (at 9 weeks) will be considered as subjects with early progression
- Subjects who die from malignant disease before the first evaluation (at 9 weeks) will be considered as subjects with early death

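### Under the Grade 4 non-hematologic DLT criterion, diarrhea on suboptimal therapy counts below 48 hours, is exempt at 48–72 hours and counts again above 72 hours; the reach is narrow, but the wording should be reconciled

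*Protocol*

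**What the plan says.** Protocol Section 10.4 defines a DLT as an event at least possibly related to study treatment, "occurring during Days 1–21 of Cycle 1", "that meets any of the following criteria". One criterion is "Any Grade 4 non-hematologic AE of any duration, with the following exception". The exception is "Grade 4 diarrhea lasting 48–72 hours in subjects who have received suboptimal anti-diarrheal therapy". The synopsis carries the same criterion and the same exception.

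Two later criteria in Section 10.4 can reach the same episode by another route: "Grade ≥ 2 nonhematological toxicity requiring systemic immunosuppressive therapy", whose examples include autoimmune disease of the bowel, and "Any treatment-related toxicity that causes the subject to discontinue treatment during Cycle 1".

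The DLT count feeds the safety run-in. Protocol Section 6.2 allows a DLT in at most one of the first six subjects before the rest of the study enrolls. Above that, the Safety Review Committee considers changing the dose of either or both drugs. Section 10.2.1 gives "DLT observed in > 1 of 6 subjects" as its example of an unacceptable profile.

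The SAP repeats the run-in text (6.3.1.1.1), counts subjects with any DLT (7.5.2) and lists DLT-associated events (7.5.3). It does not define a DLT itself.

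**The concern.** A toxicity criterion that depends on duration would normally be ordered: at the same grade and with the same management, a longer episode should not count for less than a shorter one. Here the parent criterion has no lower duration limit and its exception has one at 48 hours. The exempt zone therefore sits in the middle, with DLTs on both sides.

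The other duration limits in the Section 10.4 list run one way. Hematologic abnormalities count from 7 days, laboratory abnormalities beyond 1 week, and a Cycle 2 delay beyond 2 weeks; several Grade 3 events count if unresolved within 14 days. Only the diarrhea exception has two bounds, and no reason is given.

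The classification has three consequences:

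- **Run-in count.** With one other DLT among the six, it decides whether the count is 1 or 2.
- **The subject's own treatment.** Section 10.5.1 says a subject with a Cycle 1 DLT should stop study treatment, unless the investigator and medical monitor judge that continuing is in the subject's interest.
- **The denominator.** Section 9.1.3 replaces a run-in subject who receives less than 80% of planned Cycle 1 doses for reasons other than a DLT. An exempt subject who missed that many doses would be replaced, while a subject with a shorter episode would stay in as a DLT.

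Table 4 lists diarrhea/colitis among the immune-related events of ipilimumab, so Grade 4 diarrhea in the run-in is foreseeable.

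**Working it through.** The plan states no figure to reproduce. Section 12.1.1 says only "The sample size of 20 subjects is considered adequate on clinical grounds" and gives no operating characteristics for the run-in. The check is to apply the wording, then see where the result can matter.

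**Step 1: the Grade 4 criterion alone.** Inputs are the any-duration rule and its exception from Section 10.4, taking 48 and 72 hours as inside the window. The event is a DLT unless therapy was suboptimal and 48 ≤ duration ≤ 72 hours.

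| Duration (h) | Suboptimal anti-diarrheal therapy | Adequate therapy |
|---|---|---|
| 12, 24, 47 | DLT | DLT |
| 48, 60, 72 | exempt | DLT |
| 73, 96 | DLT | DLT |

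The middle column is not monotone in duration. The last column is, so the anomaly arises only with suboptimal therapy. The synopsis gives the same table.

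**Step 2: the whole list.** Because one criterion is enough, the exception removes an episode from one criterion only. A 60-hour Grade 4 episode on suboptimal therapy then falls as follows:

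- It needs systemic immunosuppression: DLT under the immunosuppression criterion, whatever its duration.
- It causes discontinuation of treatment in Cycle 1: DLT under the discontinuation criterion.
- Neither: exempt under these criteria, while a 24-hour episode in the same circumstances is a DLT.

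For immune-related diarrhea/colitis, Table 4 lists corticosteroids, and permanent discontinuation of ipilimumab at Grade 3 or 4. An episode managed that way meets the immunosuppression criterion. The discontinuation route is less clear if only ipilimumab stops, because Section 8.2.2 lets such a subject continue FLX475 alone and Section 10.4 does not say whether stopping one drug counts. The anomaly therefore survives for treatment-related Grade 4 diarrhea with suboptimal anti-diarrheal therapy, no systemic immunosuppression and no qualifying discontinuation.

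**Step 3: effect on the run-in.** One such episode moves the count by one subject. It crosses the threshold only if exactly one of the other five subjects has a DLT: 1/6 = 16.7% against 2/6 = 33.3%.

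Given that the episode has occurred, and assuming that the other five are independent with a common DLT probability p, the chance that it is decisive is 5·p·(1−p)⁴. The documents give no p, so a range is shown:

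- p = 0.10: 5 × 0.10 × 0.6561 = 0.328
- p = 0.20: 5 × 0.20 × 0.4096 = 0.410
- p = 0.30: 5 × 0.30 × 0.2401 = 0.360
- p = 0.40: 5 × 0.40 × 0.1296 = 0.259

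The expression peaks at p = 1/5, so the value cannot exceed 0.41. These figures are conditional on a disputed episode. They do not say how often one occurs.

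**The case against.** The strongest objection is that the exception seldom governs. The immune-related diarrhea that makes this foreseeable is also the kind that Table 4 treats with corticosteroids, so the immunosuppression criterion would count it at any duration. This stands, and it limits the point to the residual case in Step 2. It does not remove the inversion there.

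A second objection is that the committee would not apply the count mechanically. This also stands. A reader might infer that a second DLT forces de-escalation or stopping. The documents do not say so: Section 10.2.1 offers more than one in six as an example and says what the committee may recommend after reviewing all the data with the investigators. Section 6.2 is firmer that enrollment pauses, but says only that dose modification will be considered. The committee would see the duration and the anti-diarrheal treatment of the individual case.

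A third is that the window may be loose shorthand for an upper limit, which would make this a drafting slip. That is possible, and the one-way limits elsewhere in the list are consistent with it. The documents do not settle it. For the same reason, a reader should not infer that a count made under the present wording is wrong: the intended ordering is not stated, so there is no correct count to compare it with.

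Finally, the SAP records early discontinuation of the study (7.4.1 and 7.7). DLTs are still to be tabulated and listed, so the definition still bears on the report.

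**Conclusion.** The point holds in a limited form. Under the Grade 4 non-hematologic criterion as written, and only with suboptimal anti-diarrheal therapy, diarrhea is a DLT below 48 hours, not at 48–72 hours, and again above 72 hours. This follows from the text, is the same in Section 10.4 and the synopsis, and is not corrected in either document.

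A reader might go further and say that longer episodes in general are exempt. They are not: those above 72 hours count again, and those inside the window can still count through systemic immunosuppression or Cycle 1 discontinuation.

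The size is at most one subject per episode in a count of six. It matters to the threshold only alongside exactly one other DLT. If a disputed episode occurs, the chance that it is decisive is 26% to 41% for an assumed DLT probability of 10% to 40% in each of the other five subjects. No overall frequency can be given, because the documents contain no rate for Grade 4 diarrhea by Day 21, for suboptimal therapy or for durations. A rate for Grade 4 diarrhea alone would give only an upper bound.

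This is an inconsistency in a stated decision rule, with few subjects likely to be affected and a very small cost to repair.

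**What to change.** The sponsor should reconcile the any-duration wording of the Grade 4 non-hematologic criterion with the 48–72 hour window of its exception, identically in Section 10.4 and the synopsis, so that the classification is consistent across durations. The same edit should make clear how the exception relates to the immunosuppression and Cycle 1 discontinuation criteria: whether an excepted episode that meets either is a DLT, as the any-criterion wording implies, and whether stopping ipilimumab alone counts as discontinuing treatment. Which durations are exempt, if any, is the sponsor's clinical decision, and none is proposed here.

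The cost is one line in two places plus a short clarification. No data collection or sample size changes. Because the SAP still tabulates DLTs, one sentence in SAP 7.5.2 pointing to the reconciled definition would let the report state which reading was applied.
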